10.2 Adverse Event Assessment and Recording

The Investigator will probe, via discussion with the subject, for the occurrence of AEs during each subject visit and record the information in the site's source documents. For each AE, the PI should note the start and resolution dates, the severity, whether it meets the definition of an SAE (see [Section 10.1.2](#)), the relationship of the event to the study drug, the action taken regarding study drug, and the outcome of the event. Data should be transcribed from the source documents to the CRF as per the CRF instructions.

When reporting an adverse event, the event description should use the best matching terminology describing the event as found in the "Common Terminology Criteria for Adverse Events" (CTCAE, v 4.03). If an available CTCAE term fits the event well, no additional descriptors may be needed. However, the Investigator should add any necessary descriptions in order to clarify the event or to place it in an appropriate context. If an appropriate term matching the adverse event cannot be found in the CTCAE and you do not know the preferred MedDRA term, the adverse event description should include a diagnosis, sign or symptom with additional information to facilitate subsequent categorization into MedDRA coding terms.

10.2.1 Intensity

The PI must grade the severity of all reported adverse events into one of five categories: Grade 1 (Mild), Grade 2 (Moderate), Grade 3 (Severe), Grade 4 (Life-Threatening) or Grade 5 (Death related to AE). The standardized CTCAE severity grading scales for the specific type of adverse event reported must be used when a matching CTCAE term is available. If no reference to a standard grading scale applies or is immediately available, use the following guideline:

10.2.1.1 Grade 1—Mild

Persistence of any otherwise insignificant medical occurrence beyond 72 hours or any transient (< 72 hours) AE considered by the PI to be related to the study drug. No or minimal medical therapy or intervention required, hospitalization not necessary, no or little limitation in normal activities; nonprescription or single-use prescription therapy may be employed to relieve symptoms. Mild adverse events may be listed as expected consequences of the therapy for any given protocol, and standard supportive measures for such an expected event do not necessarily elevate the event to a higher grade.

10.2.1.2 Grade 2—Moderate

Mild to moderate limitation in activity, some assistance may be needed; possibly none but usually minimal intervention/therapy required, hospitalization possible.

10.2.1.3 Grade 3—Severe

Marked limitation in activity, some assistance usually required; medical intervention/therapy required; hospitalization possible or likely. [Specifically for ocular adverse events in this vision-related study, an immediately sight-threatening condition (e.g., impending corneal perforation, retinal detachment) may be categorized as Grade 3 if it would lead to total blindness in the affected eye(s).]

10.2.1.4 Grade 4—Life-Threatening

Extreme limitation in activity, significant and immediate assistance required; significant medical/therapy intervention required to prevent loss of life; hospitalization, emergency treatment or hospice care probable. This grade is used when the participant was, in the view of the PI, at substantial risk of dying at the time of the adverse event or it was suspected that use or continued use of the test article would have resulted in the participant's death. (This does not include a reaction that, had it occurred in a more serious form, might have caused death. For example, drug-induced hepatitis that resolved without evidence of hepatic failure would not be considered life-threatening even though drug-induced hepatitis can be fatal.)

10.2.1.5 Grade 5 – Death

Death related to AE.

10.2.2 Causality

The PI (or an authorized study physician) must submit an attribution for causality of the reported adverse event to the test article or procedure.

The attribution should take into account both the temporal association and any known physical, physiological or toxicological information regarding the test article that could reasonably infer causality. Causality should only be considered for the experimental test article and not for any standard study examination or diagnostic procedures. The four attribution categories are:

Unrelated	Does not follow a reasonable temporal sequence from the administration of study drug. The event or laboratory test abnormality is clearly due to extraneous causes (disease, other drugs, environment, etc.).
Unlikely Related	Does not follow a known pattern of response to study drug. Does not follow a reasonable temporal sequence from the administration of study drug. Disease or other drugs provides plausible explanation. It does not reappear or worsen when study drug is re-administered.
Possibly Related	Follows a known pattern of response to study drug. Time sequence from administration of the study drug is reasonable. Could also be explained by disease or other drugs.
Probably Related	Follows a known pattern of response to study drug. Time sequence from administration of the study drug is reasonable. Response to withdrawal clinically reasonable. Cannot be reasonably explained by the known characteristics of the participant's clinical state, environmental factors, or other therapies administered to the subject.

10.3 Serious Adverse Event Reporting

All SAEs (defined in [Section 10.1.2](#)), whether judged related or not to study medication, will be reported to the Sponsor (or designated Medical Monitor) by telephone, e-mail or facsimile within

24 hours of the Investigator becoming aware of such SAEs. Contact information and instructions for completing SAE forms are provided in the MOP.

The initial SAE Report should include, at a minimum, the following information:

- Protocol number (POT-CP121614)
- Site number
- Subject screening number, initials, gender, and date of birth
- Name of PI and investigator site address
- Details of SAE
- Criterion for classification as “serious”
- Date of SAE onset

Follow-up SAE reports should be submitted as further information becomes available, and the final SAE Report should include information on the SAE intensity, outcome, and relationship to study drug; dates of study drug administration, concomitant medications, and any other relevant information. The PI should also provide clear copies of supporting documents as necessary (e.g. hospital discharge summary, laboratory reports, autopsy reports, etc), with the subject’s personal identifiers removed. All SAEs will be followed until the acute event has resolved, even if the subject discontinues study participation prior to the resolution. The Investigator must report SAEs occurring at his/her site to the IRB/IEC as required.

10.4 Expected Adverse Events

10.4.1 Expected AE related to the test article

No ocular or systemic AE related to the test article are expected at the doses proposed in this protocol.

10.4.2 Expected AE related to the IVT injection procedure

Mild discomfort related to the injection procedure (including use of an eyelid speculum, anesthetic drops, mydriatic drops, antibiotic drops, povidone-iodine drops or flush and subconjunctival injection of anesthetic, as well as the actual insertion of the IVT needle) are expected. These procedure-related adverse events include but are not limited to: redness, mild eye pain, eye irritation, visual disturbance, abnormal sensation in the eye, etc. and will be graded as indicated in [Section 10.2.1](#).

10.5 Disease Progression

A condition considered by the PI as unequivocal AMD disease progression, such as lesion growth, lesion bleeding, lesion that exudes fluid, an RPE tear, and extensive deposition of lipid, in the study eye or fellow eye should be identified as such in the participant’s source documents. Disease progression that requires an intervention (e.g. administration of IVT anti-VEGF agents) should be recorded as an adverse event in the CRF. If an intervention is not required the progression is not considered an AE. The unequivocal nature of the disease progression must be indicated in the source documents. Normal progression or worsening of the medical condition under study (e.g. vision loss due to the progression of AMD), by itself, does not necessarily constitute an adverse event unless the change can be reasonably attributed to an action of the test article and not only to its lack of efficacy.

Disease progression to exudative AMD in the study eye or fellow eye requiring **surgical** intervention should be reported as an AESI (See Section 10.1.3). Anti-VEGF agents are **not** considered surgical interventions.

10.5.1 Withdrawal

Participants may choose to discontinue from treatment or to completely withdraw from this study for any reason at any time without penalty or prohibition from enrolling in other clinical protocols.

Participants wishing to withdraw from the study completely will be offered an early termination visit. This early termination visit will include the examinations outlined in [Section 8.3.6](#).

Participants wishing to discontinue treatment but willing to continue with other study procedures, will return to the clinical site for follow-up visits, as per protocol, every month or every two months until Month 12 and then Month 15, and a Termination Visit at Month 18.

10.6 Pregnancy in the Clinical Trial

Women of childbearing potential (WOCBP) are not excluded from the study as long as adequate birth control methods are being utilized. Prior to enrollment in the clinical trial, WOCBP must be advised of the importance of avoiding pregnancy during the trial and the potential risks associated with an unintentional pregnancy. WOCBP and males with partners who are WOCBP will be instructed to practice an acceptable method of birth control (as defined in [Section 6.3](#)) for the duration of the study. Male subjects will be counseled to avoid donating sperm after dosing on Day 1 until the final Exit visit.

During the trial, female subjects are to be instructed to contact the Investigator immediately if they suspect they might be pregnant. The study Sponsor must be contacted immediately and a decision will be made regarding continuation of the pregnant woman in the study based upon the circumstances surrounding the pregnancy. Pregnancy is not reportable as an adverse event; however, complications may be reportable. If a female subject or partner of a male subject becomes pregnant during the study, the PI should report the pregnancy to the Medical Monitor within 24 hours of being notified. The Investigator should follow the pregnancy until completion. At the completion of the pregnancy, the Investigator will document and report the outcome. If the outcome of the pregnancy meets the criteria for classification as an SAE (i.e. postpartum complication, stillbirth, neonatal death, or congenital anomaly) the Investigator should follow the procedures for reporting an SAE.

11. STATISTICAL CONSIDERATIONS

Analyses planned during the study include: 1) a primary intention to treat efficacy analysis after all subjects are randomized and complete 12 month follow up; and 2) ancillary analyses which will be conducted on 6 month follow up data and per-protocol analyses at both time points.

All statistical tests will be two-sided with a type 1 (alpha) error rate of 0.1. To understand the clinical significance of the estimated treatment effects and to aid in the interpretation of the formal hypothesis testing, two-sided 95% confidence intervals will be provided.

Descriptive summaries will include mean, standard deviation, median, and range for continuous variables and counts and percentages for categorical variables.

11.1 Populations for analysis

11.1.1 Primary Efficacy Analysis

The primary efficacy analysis will be based on a modified intention-to-treat population (mITT), which is defined as all randomized subjects who receive at least one dose of treatment and have at least one visit at or after month 2. Month 2 is the first visit on treatment at which lesion area is measured.

11.1.2 Supportive Efficacy Analyses

Per protocol (PP) efficacy analyses will include all randomized subjects who return for 12 (or 6) months of follow up.

11.1.3 Safety Analysis

All subjects who are randomized and receive at least one dose of treatment will be included in the evaluation of safety of APL-2. Patients will be grouped according to treatment received.

11.2 Statistical methods

11.2.1 Analysis of the Conduct of the Study

The number of subjects who enroll, discontinue (early discontinuation of treatment or early termination from the study), and complete the study (through 12 months after randomization) will be tabulated by group.

Reasons for early discontinuation of the treatment or early termination of from the study will be listed and summarized by treatment group. Any eligibility criteria exceptions and other protocol deviations will also be summarized by treatment group.

11.2.2 Analysis of Treatment Group Comparability

Demographic and baseline characteristics – such as age, gender, race, total lesion size, and baseline visual acuity score – will be summarized for all randomized subjects by treatment group.

11.2.3 Efficacy Analysis

The primary objective of this study is to determine if the mean annual growth of GA lesions in eyes injected with APL-2, either monthly (AM) or every other month (AEOM), is different from growth in eyes receiving sham injections (S). Growth will be assessed as change in square root lesion areas.^{32,33}

11.2.3.1 Statistical Hypothesis

The null and alternative hypotheses for this study are:

$H_0: \mu_S = \mu_{AM} = \mu_{AEOM}$ vs $H_A: \mu_i = \mu_j$ for $i \in \{S, AM\}; j \in \{AM, AEOM\}$ and where μ indicates each groups respective 12 month change in square root lesion area .

11.2.3.2 Analytic Methods

Since prior studies have demonstrated that square root area changes are independent of baseline size,^{1,2} we anticipate analysis with one factor Analysis of Variance (ANOVA) and no need for a baseline covariance correction or baseline size stratification. If the overall hypothesis of equality of group means (H_0) is rejected at the 0.1 alpha level, then group means will be compared with post-hoc Least Significant Difference (LSD) multiple comparisons. These multiple comparisons will also be conducted at the 0.1 alpha level.

11.3 Determination of Sample Size

The sample size required is based on the 12 month per protocol analysis. Thus drop out is accounted for in the sample size determination.

11.3.1 Natural history growth rates

Based on two assessments of GA growth measured with Cirrus OCT,^{32,33} we assume that in the absence of treatment average square root area lesion growth is 0.33mm/year (mean of 0.28mm/year³³ and 0.37mm/year³²) and the standard deviation of annual square root area growth is 0.21mm/year.³²

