11.3.3 Treatment efficacy and power analysis

This study is designed to detect a 30% reduction in annual square root area increase. Calculations are provided for three scenarios (Proc Power onewayanova, SAS 9.3)

Square root area change (mm)			Sample size			Power to detect a difference
AM	AEOM	S	AM	AEOM	S	
0.23	0.23	0.33	67	67	67	91%
0.23	0.33	0.33	67	67	67	91%
0.23	0.28	0.33	67	67	67	83%

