11.3.4 Drop out/Loss to follow up

We assume a 15-20% loss to follow up. Accordingly, inflation of the sample size in (d) Total N = 201÷83.5% suggests recruitment of 240 subjects should be sufficient.

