### **3.3. DETERMINATION OF SAMPLE SIZE**

With a total sample size of 201 evaluable subjects there is approximately 90% power to claim a statistically significant difference in means among treatment groups if there is a 'true' 30% reduction in annual increase of square root GA area for the APL-2 treated groups compared with the pooled sham treatment group. This assumes that, in the absence of treatment, average square root area change is  $0.33\text{mm}/\text{year}^{1,2}$ , the standard deviation of annual square root area change is

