## Statistical Analysis Plan

---

all available data in the model, has been specified in the SAP to account for missing data and this will be regarded as the primary analysis.

4. The pharmacokinetic endpoints of AUC,  $C_{max}$ ,  $T_{max}$  and  $t_{1/2}$  were specified in the protocol; however since only trough concentrations were collected throughout the study it is only possible to assess  $C_{max}$ .  $C_{max}$  should occur at Day 7 so the concentration on Day 7 will be used ( $C_{Day 7}$ ).
5. The protocol specified a standard deviation of annual square root area growth of 0.21mm/year for the sample size calculations. However in the power analysis (protocol Section 11.3.3) a value of 0.2 was used for the standard deviation.
6. The protocol refers to the first day of dosing as Day 0 (Visit 2). For reporting purposes CDISC standards will be used and therefore it is necessary to refer to the first day of dosing as Day 1. Consequently throughout the SAP Day 1 is referred to as the first day of dosing.

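### The stated power of 91%, 91% and 83% uses an SD of 0.20 where the protocol's planning SD is 0.21, and 240 randomised does not give 201 evaluable over the whole assumed loss range

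*Protocol*

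**What the plan says.** Protocol 11.3.1 takes two planning values from cited natural-history studies: "average square root area lesion growth is 0.33mm/year" without treatment, described as the mean of 0.28 and 0.37, and "the standard deviation of annual square root area growth is 0.21mm/year".

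Protocol 11.3.3 states the aim: "This study is designed to detect a 30% reduction in annual square root area increase". Its table prints group means, 67 per group and power for three scenarios (91%, 91%, 83%), computed as a one-way ANOVA in SAS. It prints no SD. Protocol Section 11 sets the level: "All statistical tests will be two-sided with a type 1 (alpha) error rate of 0.1".

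SAP 3.3 gives "approximately 90% power to claim a statistically significant difference in means among treatment groups" with 201 evaluable subjects, and there the SD is 0.2 mm/year. SAP Section 13, item 5, first notes that the protocol specified 0.21, then says: "However in the power analysis (protocol Section 11.3.3) a value of 0.2 was used for the standard deviation".

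On attrition, Protocol 11.3.4 says "We assume a 15-20% loss to follow up", divides 201 by 83.5% and settles on 240. SAP 3.3 repeats the 15-20% range and says that 240 is what is needed to obtain 201 evaluable.

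**The concern.** The power table does not follow from the SD given two subsections before it. The SAP noticed the mismatch but neither recalculated the power nor gave a reason for preferring 0.2. The only SD with a source in either document is 0.21.

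The attrition statement has a similar gap. A range of losses is assumed, but a single retention factor near its favourable end is used, and the resulting evaluable number is presented as if it held across the range.

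Both slips flatter the plan. Readers will set a non-significant overall test, or a graded result with the every-other-month arm between monthly and sham, against the stated power. The graded scenario is the most affected, and SAP 3.3 does not show it at all: it quotes only a figure near 90%.

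**Working it through.** **Inputs.** Three groups after pooling the sham arms (Protocol 11.3.2); overall F test at alpha 0.10 (Protocol 11 and 11.2.3.2); group means from the table in Protocol 11.3.3; SD 0.20 (SAP 3.3 and Section 13) or 0.21 (Protocol 11.3.1); n = 67 per group.

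**Formula.** With equal group size n, the noncentrality is λ = n × Σ(μᵢ − μ̄)² / SD². Power = P[F′(2, 3n − 3; λ) > F₀.₉₀(2, 3n − 3)], where F′ is noncentral F.

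**Sums of squares of the means**

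- Scenario 1 (0.23, 0.23, 0.33) and scenario 2 (0.23, 0.33, 0.33): Σ = 0.006667.
- Scenario 3 (0.23, 0.28, 0.33): Σ = 2 × 0.05² = 0.005.

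**Reproducing the table (SD 0.20, n = 67)**

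- Scenarios 1 and 2: λ = 67 × 0.006667 / 0.04 = 11.17; power 91.4%.
- Scenario 3: λ = 67 × 0.005 / 0.04 = 8.375; power 82.6%.

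These are the printed 91%, 91% and 83%.

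**Same calculation at SD 0.21 (n = 67)**

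- Scenarios 1 and 2: λ = 67 × 0.006667 / 0.0441 = 10.13; power 88.8%.
- Scenario 3: λ = 67 × 0.005 / 0.0441 = 7.60; power 79.0%.

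**Evaluable numbers from 240 randomised**

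- 15% loss: 240 × 0.85 = 204 (68 per group).
- 16.5% loss (the protocol's 83.5% factor): 240 × 0.835 = 200.4.
- 20% loss: 240 × 0.80 = 192 (64 per group).
- Largest loss that still leaves 201: 1 − 201/240 = 16.25%.
- To have 201 after 20% loss: 201/0.80 = 251.25, so 252 randomised.

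**Power over the assumed loss range**

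| SD | Evaluable (per group) | Scenario 1 | Scenario 2 | Scenario 3 |
|---|---|---|---|---|
| 0.20 | 201 (67) | 91.4% | 91.4% | 82.6% |
| 0.20 | 192 (64) | 90.2% | 90.2% | 80.9% |
| 0.21 | 204 (68) | 89.2% | 89.2% | 79.6% |
| 0.21 | 201 (67) | 88.8% | 88.8% | 79.0% |
| 0.21 | 192 (64) | 87.4% | 87.4% | 77.2% |

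**Rounding of the means.** The mean of 0.28 and 0.37 is 0.325, and 30% of 0.33 is 0.099. With a sham mean of 0.325, exact 30% and 15% reductions (0.2275 and 0.27625) and SD 0.21, power is 87.2%, 87.2%, 77.1% at 67 per group and 85.8%, 85.8%, 75.3% at 64 per group.

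**The case against.** The SAP discloses the mismatch, states 0.2 beside its own power figure, and declares that it supersedes the protocol on statistical methodology. On that reading its statement is internally consistent. It also claims only about 90%, and 88.8% is arguably still that. This stands as far as it goes: the printed figures that fail are the protocol's 91%, 91% and 83%. But disclosure does not supply a source for 0.2 or a figure at 0.21.

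The 0.21 is itself an assumption, taken from lesions measured by OCT, whereas the primary endpoint uses autofluorescence. The SAP's primary analysis is a baseline-adjusted repeated-measures model using all available data in the modified intention-to-treat population, not an ANOVA in completers, and its power cannot be computed from the documents. Both points are correct. They limit what any restated figure means, but they do not make the printed figures follow from the printed inputs.

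On attrition, 240 is an approximate number, the synopsis asks for 200 evaluable, and at 15% loss 240 leaves 204. That is also fair: the claim fails only above 16.25% loss, but this is most of the assumed range.

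The rounded means are ordinary two-decimal rounding and are printed openly, so they need no correction. No target power is set anywhere, so 80% is a conventional marker and not a criterion of this plan. Finally, SAP version 3.0 was written after the 12-month results had been reviewed, so the restatement affects reporting and not design.

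**Conclusion.** The concern holds. The protocol's power table was computed with SD 0.20 and contradicts the protocol's own planning value. At SD 0.21 and 201 evaluable, power is lower than the rounded figures printed by 2.2, 2.2 and 4.0 points (91 − 88.8, 91 − 88.8, 83 − 79.0). At 20% loss the gaps are 3.6, 3.6 and 5.8 points. The graded scenario is below 80% over the whole assumed loss range at SD 0.21, from 79.6% down to 77.2%. The statement that 240 gives 201 evaluable at 15-20% loss is wrong above 16.25% loss.

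These figures rest on the protocol's overall one-way ANOVA in completers, equal group sizes, the table's rounded means and SD 0.21. They do not describe the SAP's repeated-measures model. The effect is modest, but a stated power and a stated evaluable number are both wrong as written, and the correction is simple.

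**What to change.** In Protocol 11.3.3 and SAP 3.3, state the SD as 0.21 and give power as 89%, 89% and 79% with 201 evaluable, and 87%, 87% and 77% with 192 evaluable (20% loss). Show all three scenarios in the SAP, so that the graded case is visible.

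In Protocol 11.3.4 and SAP 3.3, replace the claim of 201 evaluable with the range that 240 randomised gives over 15-20% loss: 192 to 204.

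If the sponsor prefers 0.20, give its source and show the 0.21 figures beside it.

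The cost is restated text and a slightly less favourable power statement. Enrolment, design and analysis stay as they are.
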